### **Surrogate tests for the phase II substudy**

A subset of 80 patients in both groups will undergo testing for NK cell function and characteristics, blood levels of cytokines, CRP, albumin, and leukocytes. Testing will occur four weeks following surgical resection but prior to commencing the study treatment (baseline) and six months after beginning the study treatment (end point). In addition to venipuncture for measurement of CRP, albumin, and leukocytes, immunological functional assays adapted by [name] lab will be conducted on NK cell activity as well as performing a series of assessments for pro- and anti- inflammatory cytokines.

#### **i. Human NK cell cytotoxicity assay**

Human whole blood will be processed for Peripheral Blood Mononuclear cells (PBMCs) using Ficoll Paque (Stemcell). These will be used as Effector cells in an *ex vivo* NK cell cytotoxicity assay. The human NK cell sensitive tumor cell line – K562 (human leukemia) will be used as Target cells. K562 tumor cells will be harvested and labelled with 100 $\mu$ Ci of  $^{51}\text{Cr}$  (Perkin-Elmer) in the form of  $\text{Na}_2\text{CrO}_4$  for 1 hour. They will be added to the PMBCs in the 96-well plate at different effector to target cell ratios (25:1, 12:1, 6:1, 3:1). The mixture will be incubated for 4 hours prior to analysis of chromium release in the supernatant using a gamma counter (Perkin Elmer). To show NK cell specific lysis of tumor targets, NK cells will be depleted from PBMC population using CD56 microbeads (Miltenyi Biotech) in a control experiment where no killing of targets will be detected.

#### **ii. Cytokine array**

Includes IL2, IL4, IL6, IL10, IL12, IL15, IFN- $\alpha$ , IFN- $\gamma$ , TNF- $\alpha$ , GM-CSF, TGF- $\beta$ 1, and VEGF in a mix 'n match multi-analyte ELISA array (SAbiosciences, Qiagen). Serum (or plasma) will be obtained from human whole blood through centrifugation (30,000 rpm for 20mins). Human cytokines will be determined by sandwich enzyme-linked immunosorbent assay (ELISA), using the Mix 'n Match multi-analyte ELISA array from SA Biosciences. Briefly, 96-well microtiter plates arrive already coated with capture antibody. Recombinant antigens and patient samples are added to their respective wells and incubated for 2h. Samples are then washed and incubated with detection antibodies for 1h. They are again washed and incubated with Avidin-HRP for 30mins. Following a final wash, they are incubated with development substrate and stop solution and have optical density read at 450nm.

### iii. Flow cytometry

PBMCs will be isolated from whole blood using Ficoll Paque (Stemcell). Blood lymphocytes will be analyzed for total number of NK cells using CD56 and CD3 fluorescent conjugated mAb. CD69 expression (early activation marker), IFN $\gamma$  secretion (NK cell secreted cytokine in response to activation), CD107a (cell surface degranulation marker), and Granzyme B secretion (NK cell secreted cytoxic granule) will be analyzed using specific fluorescent conjugated mAb. Events will be acquired on a Beckman Coulter CyAn and data analyzed using Kaluza software (Beckman Coulter, v1.1).

Secondary outcomes of the study include compliance, adverse events, time to recurrence and/or mortality, and scores from validated questionnaires to measure quality of life, pain, depression, anxiety, sleep, and fatigue. The following validated questionnaires will be used:

Questionnaire	Acronym	Measure of
Brief Pain Inventory	BPI	Postoperative pain
Beck Depression Index	BDI	Depression
Beck Anxiety Inventory	BAI	Anxiety
Leeds Sleep Evaluation Questionnaire	LSEQ	Sleep quality
Fatigue Symptom Inventory	FSI	Fatigue
Quality of Life in Cancer Patients	EORTC QLQ-C30	Quality of life
Quality of life in Lung Cancer Patients	EORTC QLQ-LC13	Quality of life specific in lung cancer patients

Note: the entire battery of questionnaires listed above will be administered at the Ottawa site at Baseline, 1 and 2 years. Only the Pain and Sleep questionnaires will be administered at 3 week, 3, 6, 9, and 18 months. At multicentre sites, the Sleep, Fatigue, QLQ-LC13 and QLQ-C30 questionnaires will be administered at Baseline, 1 and 2 years, and only the Sleep questionnaire at 3 week, 3, 6, 9, and 18 months.

Every document provided to the patients will be available in both English and French depending on language of preference. This also applies to the questionnaires, and licenses for each of them in both official languages have been obtained. Each of the questionnaires has been validated in both English and French.

Adverse effects attributed to chemotherapy and radiation therapy will be collected using the Common Terminology Criteria for Adverse Events (CTCAE version 3.0), a validated form published by the National Cancer Institute. During follow up visits Research Coordinators should look through the study diary with the patient and inquire about the severity of any adverse or serious adverse effects. During follow up phone calls, the severity of any adverse and serious adverse events should also be assessed.

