### 2.2 Secondary Objectives

1. To assess the impact of melatonin compared to placebo on the frequency, severity, and type of adverse effects caused by post-operative adjuvant chemotherapy and/or radiation.
2. To assess the impact of adjuvant melatonin compared to placebo on quality of life (QOL), sleep, pain, anxiety, depression, and fatigue.
3. To determine the type and presence of any adverse effects induced by melatonin in comparison to placebo by chart review and interactions with patients at their study visits.
4. To compare the time to recurrence and time to mortality (up to five years) between the placebo and melatonin groups.

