## 3. Hypotheses

[figure not shown]
- a) Adjuvant melatonin will reduce the incidence of lung cancer recurrence of NSCLC two years after surgical resection.
- b) Adjuvant melatonin will reduce disease specific 2-year mortality following lung cancer resection.
- c) Melatonin will lead to a reduction in chemotherapy related toxicities and have no impact on adverse effects due to radiation therapy.
- d) Melatonin will lead to improved QOL, less fatigue, improved sleep, and have no impact on depression or anxiety in patients following lung cancer resection.

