### **6.9 Adverse Events**

An “adverse event” means any adverse occurrence in the health of a clinical trial subject who is administered a natural health product, that may or may not be caused by the administration of the natural health product, and includes an adverse reaction, a serious adverse reaction and a serious unexpected adverse reaction.

According to the Health Canada approved product monograph, expected adverse events associated with melatonin include fatigue, nausea, vomiting, and cramping. Though rare, allergic reactions have been reported. Morning fatigue may occur with greater frequency at the beginning of the study [76]. Patients should be informed that melatonin should not be consumed with alcohol, other medications or natural health product with sedative properties.

In a review of scientific literature, in very rare cases (only 9 out of 307 articles reported adverse effects), the following reactions of Melatonin were reported:

- Four cases of seizures
- Two cases of skin eruptions (skin rash)
- One patient with autoimmune hepatitis (chronic disease of the liver)
- One case of confusion
- One case of optic neuropathy (disease of the eye)
- Four cases of fragmented sleep
- One psychotic episode
- One case of nystagmus (rapid involuntary rhythmic eye movement)
- One case of headache

Given the anecdotal nature of much of this evidence, however, it is debatable whether or not Melatonin was the true cause of the adverse events reported. The adverse effects of melatonin appear to rest on a limited number of studies and case reports. However, few studies have been conducted to establish the veracity of attributing these effects to melatonin.

Interaction of melatonin with nifedipine is perhaps the best documented interaction in that it has evidence from a randomized controlled trial, albeit a small one [77].

Patients taking nifedipine and concomitant melatonin showed a decrease in blood pressure control from baseline administration of nifedipine only. Therefore baseline and follow up

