## NSCLC Adjuvant melatonin RCT

- Hemothorax
- Prolonged air leak
- BP Fistula
- SubQ emphysema
- Atrial arrhythmia
- Ischemia
- Hypertension
- CHF
- Cardiac effusion
- UTI
- Renal insufficiency
- Non-infect. diarrhea
- Constipation
- Vomiting
- Ileus (bowel obstruction)
- Confusion
- Infection
- C-difficile
- Heart block

Patients in this study may also be undergoing chemotherapy or radiation treatment. As such it is reasonable to expect that they may experience adverse events related to this treatment, which include the following:

- Febrile neutropenia
- Nausea/vomiting
- Fatigue

It is possible that in some cases the events defined above may be related to the study drug (or exacerbated by the drug). The site investigator will assess the relationship of the study drug to the events listed above and the seriousness of the event (see 6.10 Serious Adverse Events)

Patients in this study could be diagnosed with a new primary cancer while on study. If this is the case, the new primary is reported as an adverse event. However, a recurrence of the lung cancer (outcome) will not be reported as an adverse event.

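### The chemotherapy/radiation toxicity comparison rests on attributed events, with no all-cause comparison planned, although nausea, vomiting and fatigue are also expected from melatonin

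*Combined protocol and SAP*

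**What the plan says.** Secondary objective 1 (Section 2.2) compares the arms on the "frequency, severity, and type of adverse effects caused by post-operative adjuvant chemotherapy and/or radiation". Hypothesis (c) in Section 3 gives it a direction: "Melatonin will lead to a reduction in chemotherapy related toxicities and have no impact on adverse effects due to radiation therapy". Section 6.5 describes the data: "Adverse effects attributed to chemotherapy and radiation therapy will be collected using the Common Terminology Criteria for Adverse Events (CTCAE version 3.0". Secondary objective 3 covers melatonin's own effects separately: "To determine the type and presence of any adverse effects induced by melatonin in comparison to placebo".

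Section 6.9 gives lists of expected events that overlap:
- For the study drug: "expected adverse events associated with melatonin include fatigue, nausea, vomiting, and cramping".
- For chemotherapy or radiation, "it is reasonable to expect that they may experience adverse events related to this treatment, which include the following"; the list is febrile neutropenia, nausea/vomiting and fatigue.
- Fatigue is also listed as expected from lung cancer itself.

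The same section recognises the overlap: "It is possible that in some cases the events defined above may be related to the study drug (or exacerbated by the drug". It leaves the judgement to one person: "The site investigator will assess the relationship of the study drug to the events listed above". No rule is given for an event with several possible causes. Section 8 contains no adverse event analysis, attributed or all-cause.

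**The concern.** Randomisation protects a comparison of all events by arm. It does not by itself protect a count filtered by a causal judgement made after randomisation, because that judgement can respond to what the drug does. Events truly caused by melatonin can occur only in the melatonin arm. If they are recognised and left out of the chemotherapy count, they leave from one arm only. Attribution can also drift by arm without formal unblinding: Section 6.4 notes that melatonin is soporific, and Section 6.9 expects morning fatigue early on, so the clinical picture may point to the capsule more often on melatonin.

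At stake is how a result on hypothesis (c) is read. A fall in attributed nausea and fatigue could be taken to mean that patients on chemotherapy had that much less nausea and fatigue, when their total burden fell by less. No planned analysis would show the difference. The fatigue and QLQ-C30 questionnaires do not fill the gap, since they are given at baseline, 1 year and 2 years and are not timed to chemotherapy courses.

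**Working it through.** The documents give no toxicity rate, attribution probability, sample size or power for this endpoint, so there is no figure of the plan's own to reproduce. All rates below are assumptions used to test the mechanism.

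**1. Capsule-caused events are removed from the count.** Take chemotherapy-caused nausea as 50% on placebo and 35% on melatonin, and let m be the melatonin-caused risk, independent of the first. Let r be the share of capsule-only events that are recognised and removed, with no false capsule attribution on placebo.

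- All-cause rate on melatonin = 1 − (1 − 0.35)(1 − m)
- Capsule-only rate = 0.65 × m
- Attributed rate = all-cause rate − r × 0.65 × m
- Each RR is the rate divided by 0.50

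Results:
- m = 2%: all-cause 1 − 0.65 × 0.98 = 0.363, RR 0.73. With r = 1, attributed 0.35, RR 0.70.
- m = 10%: all-cause 1 − 0.65 × 0.90 = 0.415, RR 0.83. With r = 1, attributed 0.35, RR 0.70.
- m = 10%, partial recognition: capsule-only rate 0.065. With r = 0.5, 0.415 − 0.0325 = 0.3825, RR 0.765. With r = 0.2, 0.415 − 0.013 = 0.402, RR 0.80. With r = 0, RR 0.83, equal to the all-cause RR.

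Sensitivity to the rates, with a 20% relative reduction in chemotherapy-caused events, r = 1 (attributed RR 0.80) and m = 5%, 10%, 15%:
- Placebo 50%, melatonin 40%: all-cause 0.43, 0.46, 0.49; RR 0.86, 0.92, 0.98.
- Placebo 30%, melatonin 24%: all-cause 0.278, 0.316, 0.354; RR 0.93, 1.05, 1.18. At m of 10% or more the direction reverses.

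**2. Attribution differs by arm.** Let the all-cause rate be 50% in both arms, so that the true RR is 1. The chance of a significant result is at an assumed two-sided 0.05, for 80, 160 and 320 treated patients per arm. The number who will receive chemotherapy is not given; 320 is the full arm.
- Probability of attribution to chemotherapy 0.9 on placebo and 0.8 on melatonin: 45% v 40%, RR 0.89; chance 9%, 15%, 25%.
- 0.9 and 0.7: 45% v 35%, RR 0.78; chance 25%, 45%, 73%.

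**3. Attribution is equal in both arms.** With a common probability q, attributed RR = (q × rate on melatonin) / (q × rate on placebo), and q cancels. The attributed RR equals the all-cause RR; only the absolute difference shrinks, by the factor q.

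**The case against.** The strongest case on the other side has five parts.

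- **The attributed figure answers the stated question.** Objective 1 and hypothesis (c) concern toxicity caused by the cancer treatment. If 35% v 50% is the true chemotherapy-caused contrast, RR 0.70 is the right answer to that question. This stands. A reader might infer that hypothesis (c) would be answered wrongly in the drug's favour. The documents do not support that in general: the difference is between chemotherapy-caused toxicity and total symptom burden. Attribution that differs by arm would distort the answer even to the narrower question, but nothing in the documents shows that it will.
- **Blinding.** Section 6.4 blinds patients, physicians and the coordinator. Equal blinded attribution leaves the relative risk unaffected, as step 3 shows. This stands, and a claim that blinding is no help would be wrong. It does not cover events correctly recognised as capsule-caused, nor judgement prompted by sedation.
- **The plan does not sort each event into objective 1 or objective 3.** One might read the two objectives as exclusive, but no section says so, and Section 6.9 allows a listed event to be exacerbated by the drug. Dual-cause events kept in the chemotherapy count cause no gap. The plan is silent on this, and the concern is limited accordingly.
- **All adverse events are recorded.** Section 6.5 lists adverse events without restriction as a secondary outcome and has staff ask about the severity of any event; Section 6.9 records all of them. This makes the fix cheap. It is not a planned comparison, and Section 6.5 applies CTCAE only to attributed effects.
- **The overlap is partial.** The chemotherapy/radiation list in Section 6.9 is not exhaustive. The prior evidence in Section 1 also names leucopenia, thrombocytopenia and hypotension, none of which is among the expected melatonin effects in Section 6.9.

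**Conclusion.** The concern holds in a limited form. For nausea, vomiting and fatigue, the comparison behind objective 1 depends on a causal judgement made after randomisation, the protocol's own lists give those symptoms more than one expected cause, and no all-cause comparison is planned. The attributed contrast can then overstate the reduction in total symptom burden, either because capsule-caused events are removed or because attribution differs by arm.

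The size cannot be derived from the documents. Under the assumed 50% v 35%, with melatonin-caused nausea of 2% to 10% and full recognition of capsule-only events, an attributed RR of 0.70 goes with an all-cause RR of 0.73 to 0.83: a 30% reduction against 27% to 17%. The low end is negligible, and the gap closes entirely if no capsule-only event is recognised. The melatonin-caused rate is the least certain input, since Section 6.9 lists nausea as expected but gives no frequency.

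The concern does not reach febrile neutropenia or the haematological toxicities. It affects a secondary objective and is a cheap improvement to the plan, not a flaw in the primary analysis.

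**What to change.** In Sections 2.2 and 6.5, with a matching sentence in Section 8:

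- Grade every recorded adverse event on CTCAE v3.0, whatever its attributed cause.
- Make the main toxicity comparison the worst grade per event type by randomised arm, regardless of attribution.
- Show it for all randomised patients with adverse event follow-up, and also for those who start chemotherapy and those who start radiation. State that the treated subsets may be defined after randomisation, because capsules can begin at discharge, so randomisation may not fully protect them.
- State the limits set by Section 6.9: adverse event tracking stops at recurrence and omits patients who never start capsules.
- Keep the attributed analysis as supportive, and keep attribution for reporting under Section 6.10.

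The events are already recorded to two years and their severity is already asked about, so the cost is wording plus CTCAE grading of events not attributed to chemotherapy or radiation. The downside is more background noise, since all-cause counts include symptoms of the cancer itself.

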## 6.6 Follow-up Calls/Visits and Data Collection

Information will be captured by the research coordinator who will fill in the case report forms and supervise patients' completion of the questionnaires at baseline, 3 weeks, 3 months, 6

## NSCLC Adjuvant melatonin RCT

months, 9 months, 1 year, 18 months and 2 years. Information regarding the results from chest x-rays or CT scans, chemotherapy and/or radiotherapy treatment, recurrence and past medical history/concomitant medications will be captured from the patient's chart. All other information will be captured by the research coordinator through telephone conversations and follow up visits with the patients.

The research coordinator will make a follow up phone call once per week for the first two weeks and then as needed for the one year while the patient is on the study drug. During telephone conversations, the research coordinator will assess study compliance and any adverse or serious adverse events. Information regarding these phone calls will be captured in the patient's study records.

At follow up appointments, the research coordinator will provide the patient with study drug refills (up to the 1-year mark), provide quality of life questionnaires, monitor any adverse or serious adverse events and monitor compliance. Compliance will be monitored during a brief interview, and by checking for left over pills. Patient self-report is an acceptable measure of compliance if counting pills is not feasible. Patients will be asked at each follow-up phone call and visit if they have missed any capsules. Patient reports of start and end dates of the capsules will also be used to determine compliance.

The study will be extended to include follow up periods past the initial follow up period of two years. Specifically, patient follow up times will be extended to include follow ups with all patients enrolled on study beginning in 2007. Patients' records will be tracked to determine whether they experienced a recurrence or death. Participants will be followed until they either reach the five year maximum or until 2 years after the last participant was enrolled in the study. As such, each patient will have a varying follow up period (with a range of 2-5 years).

Extension of follow ups past the two year time point will be conducted as follows:

Patients' medical records will be reviewed in order to record cancer recurrence or death. Should the information not be available in the medical records, their records will be requested from the Canadian Cancer Registry. If patient information cannot be found in the registry, surgeons will be asked to follow up with the patient's GP in order to find out whether they had a recurrence or died. If the patient's GP does not have this information, but directs us elsewhere, or if the medical records indicate that the patient was discharged to another facility (eg: another hospital), this facility will be contacted. At the facility's request, the signed patient consent form will be provided in order for them to release the information on the patient's death or recurrence. If this information cannot be retrieved through searching patient records in any of the above methods, patients will be contacted directly. Patient contact will begin with a letter and brief questionnaire to the last known address (letter and questionnaire provided by the coordinating centre) requesting an update on patient health status. If the patient does not respond to the letter, the study coordinator will contact the patient at their last known telephone number, and ask for a health status update. If the patient cannot be contacted, and all other options are exhausted, the study coordinator will contact the patient's next of kin (telephone script provided by the coordinating centre). Should we be unable to follow up in any of the above methods, participants

will then be considered lost to follow up. Sites should ensure that the letter, questionnaire, and telephone script receive REB approval prior to use.

Patients who 1) withdrew from the trial before starting the intervention, or 2) were enrolled but considered to be screen fails (did not meet inclusion criteria) and did not start the intervention, or 3) recurred within the first two years, will be followed only for outcome data (recurrence and/or mortality). The “Follow-up for Withdrawals and Screen Fails (who did not start intervention)” CRF will be completed annually for these patients (up to 5 years post-op). Adverse events will not be tracked for these patients.

## **6.7 Standardization**

All study personnel, including surgeons, oncologists, nurses, and the research coordinator will undergo group familiarization and orientation of the study protocol to ensure comprehensive awareness of the study procedures. There will be an initial orientation for the study team at each site before the trial begins. Once recruitment is active and the trial is underway retraining and/or site visits will be performed as needed.

